6.2. Study Flowchart

[figure not shown]

Figure 4 - Clinical Study Flowchart

6.3. Study population

The study population consists of adult patients with metastatic bone tumors undergoing radiofrequency tumor ablation with the SPINERY RF device.

6.3.1. Inclusion criteria

Participants are eligible to enroll in the study only if *all* the following criteria apply:

1. Patients with painful metastatic malignant lesions involving bone;
2. Patients, candidates to standard therapy, in which the RF ablation can be performed in combination with the Standard Therapy in accordance with the Investigator's indications;
3. Patients who have failed, not candidates or refuse Standard Therapy (chemotherapy or radiotherapy);
4. Patients with metastatic tumor size compatible with the expected ablation dimensions as reported for SPINERY devices in the IFU;
5. Patients with localized pain resulting from not more than two sites of symptomatic metastatic disease;
6. Patients that do not have evidence of impending fracture;
7. Patients with metastatic lesions targeted for treatment located in the thoracic and/or lumbar vertebral body(ies), peri-acetabulum, iliac crest, and/or sacrum - no restrictions on location of lesion;
8. Patients with BPI-Report worst pain score $\geq 4/10$ at the target treatment site within the past 24 hours;
9. Patients with Karnofsky score ≥ 40 at enrollment;
10. Patients willing and able to provide a signed and dated informed consent, comply with the study plan, follow up visits and phone calls;
11. Patients at least 18 years old at the time of informed consent.

6.3.2. Exclusion criteria

Participants are excluded from the study if *any* of the following criteria apply:

12. Patients implanted with heart pacemaker or other implanted electronic device;
13. Patients with previous mechanical bone stabilization in the vertebral body to be treated;
14. Use of SPINERY RF device in vertebral body levels C1-C7;
15. Multiple myeloma, solitary plasmacytoma, or primary malignant lesions in the index vertebra or bone;
16. Active or incompletely treated local infection at the planned treatment site(s) and/or systemic infection;
17. Planned treatment site(s) accompanied by objective evidence of secondary radiculopathy or neurologic compromise;
18. Planned treatment site(s) associated with spinal cord compression or canal compromise requiring decompression;
19. Fractures due to prostatic cancer or other osteoblastic metastases to the spine. Metastatic lesions originating in the prostate that are osteolytic or of mixed origin are eligible for the study;
20. Pregnancy, breastfeeding, or plan to become pregnant during the study duration;
21. Concurrent participation in another clinical study that may add additional safety risks and/or confound study results;
22. Any condition that would interfere with the subject's ability to comply with study instructions or might confound the study interpretation.

Exclusion criteria have been identified thanks to literature review concerning RF ablation contraindications¹:

- Criterion nr. 9 originates from the possibility of interferences between SPINERY and the implanted electronic device, which might be damaged by RF emission
- Criteria nr. 10-12-13-14-15-16 specify pathologies and conditions, which might confound study results interpretation
- Criterion nr. 11 originates from the incompatibility of vertebral bodies C1-C7 with SPINERY procedure in terms of shape and limited dimensions
- Criteria nr. 17-18 have been included for ethical reasons and to guarantee subjects' protection
- Criterion nr. 19 refers in general to subject's conditions which, according to physician's assessment, might not allow to comply with study procedures and/or might confound results interpretation

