The EQ-5D descriptive system consists of 5 dimensions: mobility, self-care, usual activities, pain/discomfort, and anxiety/depression. Each dimension has 5 levels of severity: no problems, slight problems, moderate problems, severe problems and extreme problems. The subjects are asked to indicate their health status by selecting the most appropriate statement in each of the 5 dimensions.

The EQ VAS records the respondent's self-rated health on a 20 cm vertical, visual analogue scale with endpoints labelled as 'the best health you can imagine' and 'the worst health you can imagine'. This information can be used as a quantitative measure of health as judged by the individual respondents.

The EQ-5D can be completed by the subject, in-person interview, or by phone interview by the Principal Investigator or qualified (delegated) designee.

Adverse Events Assessment

Any adverse event meeting the definition of device, therapy and/or procedure related, as well as all device deficiencies that occur from enrollment through subject discontinuation from the study will be collected.

All device, therapy and/or procedure-related adverse events will be collected for this study from enrollment to the end of the study, including events related to:

- The device components and/or procedure (Bone Access Kit, Probe, generator, etc.)
- Surgery or anesthesia regarding the initial or repeat procedure

Any adverse event due to the device, detected during the ablation procedure and/or during follow-up, will be recorded and evaluated through a dedicated case report form. The case report form will include at least the following information: date of the event, diagnosis or description of the event, severity assessment, treatment, outcome and date of resolution. The investigator is responsible for the detailed recording of the adverse event through the dedicated case report form and for the communication of the adverse event to the Sponsor.

The clinical course of each adverse event will be followed by the physician until resolution or until the subject's participation in the study is discontinued.

Deviations

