6.5.2. Withdrawal of Participants from Study Treatment

Each participant has the right to withdraw from the study at any time. In addition, the investigator may discontinue a participant from the study at any time if the investigator considers it necessary for any reason including:

- Pregnancy

- Ineligibility (either arising during the study or retrospective having been overlooked at screening)
- Significant protocol deviation
- Significant non-compliance with study requirements
- An adverse event which requires treatment discontinuation, such as adverse events related to complications during anesthesia procedure performed before RF ablation treatment, leading to the impossibility to treat the subject with SPINERY (for example inability of the patient to tolerate required level of anesthesia)
- An adverse event which results in inability to continue to comply with study procedures, that is any adverse event, which is related or not to SPINERY device and impedes the subject from attending to scheduled follow-up visits
- Disease progression which results in inability to continue to comply with study procedures, because it requires reintervention through ablation or other treatments in order to stop the progression; possible reintervention might not allow to conclude study procedures and might confound results interpretation
- Need for a second ablation procedure with SPINERY RF device or other similar devices, as per clinical judgment
- Consent withdrawn
- Lost to follow up

If a participant is withdrawn due to an AE/SAE, every attempt will be made by the investigator to obtain follow-up information about the AE/SAE until resolution or a determination that the AE/SAE will not be resolved.

If the participant withdraws consent for disclosure of future information, the sponsor may retain and continue to use any data collected before such a withdrawal of consent.

If a participant withdraws from the study, he/she may request destruction of any samples taken and not tested, and the investigator must document this in the site study records.

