10. STATISTICS

10.1. Description of Statistical Methods

All the analyses will be performed according to ITT principle.

The PPT analysis will be performed as secondary.

Sample size calculation was performed using the “proc power” in SAS v.9.4 software (Cary, NC, USA).

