10.2. Number of Participants

Approximately 52 patients will be enrolled in the study.

A sample size of 36 successfully treated subjects who complete the 3-months period of follow-up will allow to detect a difference between the pre-treatment and post-treatment means of worst pain score collected from the BPI equal to 2 points (e.g., from 7 to 5 points), assuming that the SD of the scores is equal to 3 and the correlation between measurements at different time periods is 0.3, and with two-tailed alpha = 0.05 and study power of 0.90. Such a 2-points difference is considered as the minimally important difference for the worst pain rating of the BPI (Corli O et al, 2010: p.51; *Misurare il dolore nel paziente con cancro nella ricerca e nella clinica*; Mathias SD et al, 2011; 9:72-78; J Support Oncol). Taking into account about 30% of patients' attrition from treatment through the pain assessment at 3 months, 52 subjects will be enrolled in the study. Sample size calculation was performed using the “proc power” in SAS v.9.4 software (Cary, NC, USA).

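### Section 6.5.2 lets a treated patient be discontinued for ineligibility that arises or is found after the ablation, and nothing then requires the 3-month pain score

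*Combined protocol and SAP*

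**What the plan says.** Section 6.5.2 lists grounds on which the investigator may discontinue a participant from the study at any time. One is "Ineligibility (either arising during the study or retrospective having been overlooked at screening". Neither part of it is confined to patients not yet treated. Treatment is one ablation on Day 0 (6.1, 6.4.3), so almost all study time lies after it.

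In 6.3.2, criterion 22 covers any condition that would interfere with the patient's "ability to comply with study instructions or might confound the study interpretation". It has no time point, and the note under the list (where the numbering runs three lower) leaves it to the physician's assessment. Criterion 16 includes systemic infection, with no link to the treatment site.

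On follow-up, 6.4.4 says that related adverse events "as well as all device deficiencies that occur from enrollment through subject discontinuation from the study will be collected", while its next sentence runs collection of related events to the end of the study. Section 6.5.2 adds: "If a participant is withdrawn due to an AE/SAE, every attempt will be made by the investigator" to obtain further information on that event. Section 6.5.3 keeps treated patients in follow-up when a site is closed, but no such sentence covers a patient who is discontinued individually.

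Section 10.1 states: "All the analyses will be performed according to ITT principle", with PPT secondary. Neither set is defined, and no method for missing scores is given.

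**The concern.** With one treatment session, eligibility can only act as a gate before that session. Once the ablation has started, a patient found ineligible has still been treated, and the usual consequence is a recorded deviation and possible exclusion from the per-protocol set. Here the consequence can be removal from the study.

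The person who decides is the treating investigator in a single-arm study, who knows the patient's course. A catch-all criterion, or a second look at the screening data, can be used when the patient is doing badly. The 3-month BPI is then never collected, and an ITT label cannot supply it. The ITT data drift towards the per-protocol data, and the mean change drifts towards benefit. For the co-primary safety endpoint the exposure is narrower: new events after removal may be missed. With 52 patients, each one is 1/52 = 1.9 percentage points of that endpoint.

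**Working it through.** **Inputs.** From 10.2: SD of scores 3, correlation between time points 0.3, difference 2 points, "two-tailed alpha = 0.05 and study power of 0.90", 36 treated completers, about 30% attrition, 52 enrolled. From 6.3.1: baseline worst pain at least 4 on the 0–10 scale. Assumed, because the documents do not say: the number of patients removed, a true mean change of 0, normally distributed scores, and the correlation of 0.3 between every pair of visits.

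**Step 1: the plan's own figures.** SD of change = 3 × √(2 × (1 − 0.3)) = 3.55. Exact paired-t power for 2 points is 0.899 at n = 35 and 0.908 at n = 36, so 36 is right. 36 / 0.7 = 51.4, rounded up to 52. Both figures reproduce. The plan therefore tolerates 52 − 36 = 16 patients (30.8%) without a 3-month score, counted from treatment onward.

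**Step 2: the margin.** With n = 36 the standard error is 3.55 / 6 = 0.592. An observed mean change of about −1.20 is significant. With no true effect and no removal, a significant reduction occurs in 2.5% of trials.

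**Step 3: what an investigator could select on.** The 3-month change is not known when a patient is removed before that visit. The 1-month BPI is known. Under a common correlation of 0.3:

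- Covariance of the 1-month change with the 3-month change = 9 × (0.3 − 0.3 − 0.3 + 1) = 6.3. Divided by the variance 12.6, the correlation is 0.5, so the shift is half of that under perfect foresight.
- Covariance of the 1-month score with the 3-month change = 9 × (0.3 − 0.3) = 0, so there is no shift.

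**Step 4: simulation.** Remove the worst patients and run a one-sample t-test on the remaining 36.

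| Selection on | 2 of 38 removed: shift; false benefit | 4 of 40 removed: shift; false benefit |
|---|---|---|
| 3-month change itself | −0.38; about 12% | −0.67; about 27% |
| 1-month change | −0.19; about 5.5% | −0.34; about 9% |
| 1-month score | 0; 2.5% | 0; 2.5% |

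Repeated runs of the 1-month-change case with 2 removed gave 5.3% to 5.5%.

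**Step 5: why the first row is a ceiling.** It needs knowledge of the future outcome. It also implies that the two removed patients worsened by 0.38 × 36 / 2 = 6.8 points on average, whereas entry at 4 or more on a 0–10 scale caps worsening at 6.

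**The case against.** **Criteria worded for entry.** A reader might infer that patients who develop neurologic compromise, impending fracture, further painful sites or a falling Karnofsky score after ablation can be removed for failing the matching criterion. The documents do not support stating that as fact. The inclusion criteria, such as "Patients that do not have evidence of impending fracture", govern who may enrol, and Karnofsky is fixed at enrolment. Criterion 17 reads "Planned treatment site(s) accompanied by objective evidence of secondary radiculopathy or neurologic compromise"; criterion 18 and the local part of 16 are likewise tied to planned sites. Table 3 schedules eligibility at baseline only. This part of the objection stands. What remains is criterion 22, systemic infection, and the retrospective part of the rule.

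**A pre-treatment reading.** Consent and procedure need not share a day, and lesion compatibility is checked again on Day 0, so ineligibility arising during the study could mean the interval before ablation. That is plausible, but the text does not say so, and an oversight at screening can come to light at any time.

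**Safety is followed anyway.** A reader might infer that the safety status of removed patients is simply unknown. That goes too far. An event that has already happened must be recorded (8.2.1). Sections 8.2.1 and 8.2.2 have events followed to resolution, stability or explanation, including device effects that lead to withdrawal. Only new events after removal are exposed, and the two collection periods in 6.4.4 conflict on that point.

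**ITT is primary.** Leaving the study is not deletion from the analysis set, so the rule does not by itself overturn ITT. But with no set definition and no missing-data method, nothing replaces the absent score.

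**Other exits exist.** Section 6.5.2 also allows discontinuation for adverse events, progression, a second ablation, significant deviation or any other reason. Closing one ground alone would achieve little. This stands, and the fix is widened for it.

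**Conclusion.** The point holds as a defect in 6.5.2. Its wording allows a treated patient to be discontinued as ineligible before the 3-month BPI, at the discretion of an investigator who knows the course, and no provision secures the score or surveillance for new events afterwards.

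The size is illustrative. With 2 to 4 patients removed and no true effect, a realistic early signal (the 1-month change) raises the false-benefit rate from 2.5% to about 5.5% to 9%. The figures of 12% and 27% are upper bounds that need foresight of the outcome, and selection on the 1-month score does no harm under the assumed correlations. The documents do not say how many such removals would occur. They do not show that the site-specific or enrolment-worded criteria would be applied again, or that events already seen would be lost. Because the study is pivotal for CE marking and the repair is small, it should be made.

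**What to change.** In 6.5.2, limit ineligibility as a ground for discontinuation to the time before the SPINERY procedure starts. Then add:

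> After the procedure has started, ineligibility, whether newly arisen or found in retrospect, is recorded as a deviation and affects the PPT set only if it was present at entry. Every treated patient, whatever the discontinuation reason in this list, stays in scheduled BPI and adverse event follow-up unless consent is withdrawn or the patient is lost to follow-up, and stays in the ITT and safety analyses.

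Reconcile the two adverse event collection periods in 6.4.4. The ITT definition and the handling of scores that are still missing need their own text in Section 10, since they concern every withdrawal route.

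The cost is a few sentences and some extra follow-up contacts in patients already enrolled. The required sample size does not change, and the text governs study follow-up only, not clinical care. The estimates may become slightly less favourable.

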6.3.3. Vulnerable populations

In this Clinical Investigation no vulnerable subjects will be enrolled. The vulnerable subjects are those described in the ISO 14155:2020 (paragraphs 3.55 and 5.7) and in MDR 2017/745 (Annex XV, Chapter II, paragraph 3.6.3).

¹ Cazzato et al, Spinal Tumor Ablation: Indications, Techniques, and Clinical Management, Tech Vasc Interv Radiol, 2020 Jun;23(2):100677; Thanos et al., Radiofrequency ablation of osseous metastases for the palliation of pain, Skeletal Radiol. 2008 Mar;37(3):189-94; Moynagh et al., Thermal Ablation of Bone Metastases, Semin Intervent Radiol. 2018 Oct;35(4):299-308; Study protocol "OPuS One Clinical Investigation Plan" of clinical study "OsteoCool Tumor Ablation Post-Market Study (OPuS One)"

6.4. Study procedures

6.4.1. Informed Consent

The Investigator is responsible for and will obtain informed consent from each subject in the study, in accordance with the UNI EN ISO 14155, and the current version of the Declaration of Helsinki.

All subjects invited to participate in the study are entitled to make their voluntary decision based on all currently available information provided to them by the Investigator/designee.

The participant must personally sign and date the latest approved version of the informed consent form before any study specific procedures are performed.

The participant must personally sign and date the latest approved version of the informed consent form before any study specific procedures are performed.

The Principal Investigator(s) at each site will ensure that the participant is given full and adequate oral and written information about the nature, purpose, possible risk(s) and benefit(s) of the study. The participant must also be notified that he/she is free to discontinue from the study at any time. The participant will be allowed as much time as wished to consider the information, and the opportunity to question the Investigator, their general physician or other independent parties to decide whether they will participate in the study. Written Informed Consent will then be obtained by means of dated signature of the participant and of the person who presented and obtained the informed consent. The person who obtained the consent must be suitably qualified and experienced and have been authorized to do so by the Principal Investigator. A copy of the signed Informed Consent will be given to the participant; the original signed form will be retained at the study site.

6.4.2. Eligibility Assessment

Eligible subjects are recruited among patients with metastatic bone tumors referred to one of the clinical centers. Potential participants are evaluated before enrollment based on inclusion and exclusion criteria.

6.4.3. Schedule of visits

Following signature of the informed consent, participants are enrolled in the study and perform the following study phases, as detailed in Table 1.

Enrollment and baseline visit. The eligibility criteria required by the protocol for participant's enrolment are assessed and evaluated and a comprehensive visit is performed to collect baseline parameters.

SPINERY Procedure. Patients are treated with RF ablation using SPINERY device. The use of bipolar or monopolar cooled needles or their combination is at physicians' discretion. More information is available in the instruction for use provided to each site.

Follow-up. Patients are followed-up within 24 hours from the RF ablation procedure, before the hospital discharge, and then after 1 month, 3 months and 12 months from the procedure.

	Enrollment Baseline	SPINERY procedure (Day 0) ²	Post- Procedure (within 24 hours)	1 month Follow-up (± 7 days)	3 Months Follow-up (±10 days)	12 Months Follow-up (±30days)
Informed Consent Form ¹	X					
Inclusion/Exclusion Criteria	X					
Medical History with Demographics	X					
Physical Examination	X		X		X	
Karnofsky Performance Scale	X					
PI assessment of local tumor control (optional)		X		X	X	X
Concomitant pain medications	X	X	X	X	X	X
BPI (Short Form) – includes worst pain score in the past 24 hours	X			X	X	X
EQ-5D-5L ³	X			X	X	X
Adverse Events Assessment	X	X	X	X	X	X
Deviations	X	X	X	X	X	X
Usability Assessment		X				
Tumoral lesion compatibility (clinical estimate)	X	X				
1) Informed consent must be obtained prior to performing any study-specific procedures. 2) Baseline Visit, Enrollment Visit and procedure can occur on the same day. 3) EQ-5D-5L is a standardized instrument for measuring generic health status						

Table 3 - Schedule of Visits

The attendance of subject to follow-up visits will be promoted by agreeing in advance on the schedule of visits with each subject. In addition, each subject will be contacted by phone a few days before the scheduled follow-up visit by the center to remember the need and the importance of attending the forthcoming control visit.

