Objective(s), primary and secondary	
Primary objectives:
 
 1. To demonstrate that SPINERY RF device is effective in short-term (3 months) pain reduction in patients affected by metastatic bone tumors involving the vertebral bodies, sacrum, iliac crest and peri-acetabulum with indication for standard therapy and in patients who have failed, not candidates or refuse standard therapy; 2. To demonstrate that SPINERY RF device is safe in the RF ablation treatment of metastatic bone tumors, without causing device-related adverse events including, in particular, nerve injury; 
Secondary objectives:
 
 1. To demonstrate that SPINERY RF device is effective in long-term (up to 12 months) pain reduction in patients affected by metastatic bone tumors in the areas of vertebral bodies (thoracic and/or lumbar), sacrum, iliac crest and peri-acetabulum; 2. To demonstrate safety in relation to usability; 3. To demonstrate the procedural performance in terms of a short learning curve.
Hypotheses, primary and secondary	
Primary hypothesis:
 
 - BPI Brief Pain Inventory scale performance in terms of palliative treatment: 
H0: $\mu_c = 0$
 
HA: $\mu_c \neq 0$
 
Where μ_c is the mean change from baseline to the 3-month visit in worst-pain score.
 
No formal hypotheses for the remaining objectives.

Risks and anticipated adverse device effects to be assessed	Risks of innovative device SPINERY are the same of the state-of-the-art technology: 
 - Carbonization - Post-operative pain

	
 - Limited/uncomplete treatment due to anatomical peculiarities - damage to surrounding tissue through iatrogenic injury - Nerve injury including thermal injury, puncture of spinal cord or nerve roots potentially resulting in radiculopathy, paresis, and paralysis - Pulmonary embolism - Hemothorax or pneumothorax - Infection - Unintended puncture - Hemorrhage - Hematoma
Design of the clinical investigation	
Clinical development stage	
Pivotal confirmatory.
 
Justification: pre-market study for demonstration of conformity of the device with the Essential Requirements for CE-marking.

Design type	Prospective, Single arm, Multicenter
Control group	No control group

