5. ENDPOINTS

5.1. Primary Endpoints

The primary endpoints of the study are:

- Change of Worst Pain Score expressed as average reduction of 2 BPI (Brief Pain Inventory) scores: Thoracic/Lumbar/ Peri-acetabulum/Iliac Crest/Sacrum RF Ablation [Time Frame: Baseline vs. 3 months];

Change in pain will be calculated as:

$$\mu c = \text{worst-pain 3-month} - \text{worst-pain baseline}$$

A negative average value for change in pain represents a lowering of the subject's pain score (an improvement, or reduction in pain) and a positive value represents an increase in the subject's pain score (a worsening or increase in pain)

Worst pain score at the target treatment site will be collected from the BPI in the past 24 hours.

- Completion (%) of the ablation procedure without device-related adverse events including in particular nerve injury [Timeframe: Post-procedure, 3 months].

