7.3. Concomitant Medication

There are no restrictions to prior or concomitant medications before or during the study. The specific concomitant medications listed below should be documented as concomitant medications and will be updated at each visit:

- Osteoporosis medication(s): antiresorptive medications (e.g., bisphosphonates, parathyroid hormone (PTH), calcitonin), calcium, and vitamin D.
- Steroid(s): any steroid use, including steroid inhalers
- Oral narcotics in the last 24 hours. This information will be converted to oral morphine equivalent dose (OMED) (including transdermal patches)

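### For patients whose baseline visit precedes Day 0, pain change before the ablation can enter the primary change score, because no worst-pain score is scheduled on Day 0

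*Combined protocol and SAP*

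**What the plan says.** Table A (Synopsis) and Table 3 (section 6.4.3) carry a row for "BPI (Short Form) – includes worst pain score in the past 24 hours". It is marked at Enrollment/Baseline and at 1, 3 and 12 months. It is not marked under the procedure (Day 0) or the post-procedure visit. Concomitant pain medication, by contrast, is marked at both baseline and Day 0.

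The only statement on the timing of baseline relative to the procedure is footnote 2 of both tables: "Baseline Visit, Enrollment Visit and procedure can occur on the same day". The three later follow-up visits have windows of ±7, ±10 and ±30 days.

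Section 6.4.3 lists the enrollment and baseline visit as a phase of its own, at which "a comprehensive visit is performed to collect baseline parameters". Inclusion criterion 8 (section 6.3.1) requires a worst-pain score of at least 4/10 "at the target treatment site within the past 24 hours", and eligibility is marked at Enrollment/Baseline only.

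Section 5.1 defines the primary endpoint as the 3-month score minus the baseline score: "Worst pain score at the target treatment site will be collected from the BPI in the past 24 hours". The Synopsis tests against zero a quantity that "is the mean change from baseline to the 3-month visit in worst-pain score". The study has one arm and no control group. On medication, section 7.3 says: "There are no restrictions to prior or concomitant medications before or during the study".

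**The concern.** The primary analysis reads the mean change from baseline as the effect of the device. That reading needs a baseline score that describes pain just before ablation. The schedule secures this only for patients whose baseline visit and procedure share a day, which footnote 2 allows but does not require.

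For the others, pain may change between the two dates for reasons unrelated to the ablation. Analgesics may be changed freely, and inclusion criterion 2 admits patients who also receive standard therapy. Disease progression could move pain the other way. If such a change lasts to month 3, it lies inside the primary estimate. A control arm would share the drift and allow it to be subtracted; this design has none.

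The plan already records pain medication on Day 0, so it would document a medication change in the gap without a pain score to set beside it.

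**Working it through.** **1. The plan's own figures (section 10.2).** Inputs: SD of scores 3, correlation 0.3, difference 2 points, two-sided alpha 0.05, power 0.90, attrition about 30%.

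- SD of change = 3 × √(2 × (1 − 0.3)) = 3.550.
- Paired t-test, noncentral t: power is 0.8993 at n = 35 and 0.9077 at n = 36, so 36 are needed.
- Attrition: 36 / (1 − 0.30) = 51.4, rounded up to 52.

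Both planned numbers reproduce.

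**2. What the endpoint contains.** For each patient,

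3-month − baseline = (3-month − Day 0) + (Day 0 − baseline).

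For a same-day patient the second term is zero. For a patient with a gap it is the pre-ablation change. If that change persists to month 3, it shifts the endpoint by its full amount. If it wears off, the first term cancels it and nothing is added. The bias in the mean is therefore

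δ = (share of patients with a gap) × (mean pre-ablation change in them) × (fraction persisting to month 3).

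The documents give none of these three factors.

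**3. Effect on the test, for assumed values of δ.** SE = 3.550 / √36 = 0.592. The smallest significant mean fall is 2.030 × 0.592 ≈ 1.20 points. With no device effect, the rejection probability comes from the noncentral t with 35 degrees of freedom and noncentrality δ / 0.592:

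| Persisting whole-sample mean fall δ | Noncentrality | Rejection probability |
|---|---|---|
| 0 | 0 | 5% |
| 0.25 | 0.42 | 7% |
| 0.5 | 0.85 | 13% |
| 1.0 | 1.69 | 38% |
| 1.5 | 2.54 | 69% |

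**4. If only half the patients have a gap** (persistence complete, SD of change held at 3.55): a 0.5-point fall in them gives δ = 0.5 × 0.5 = 0.25, or 7%. A 1.0-point fall gives δ = 0.5 × 1.0 = 0.5, or 13%.

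**5. The other direction.** A persisting whole-sample worsening of 0.5 points before ablation would turn a 2-point fall into 2 − 0.5 = 1.5. Power would then drop from 91% to 69%.

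**The case against.** Several points on the other side stand.

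- A reader might infer that no patient has a Day 0 score. The documents do not support that: when the visits share a day, the baseline score is the Day 0 score.
- A reader might also infer that every pre-ablation change passes in full into the device effect, or that the result is biased in the sponsor's favour. Neither follows. Only change that persists to month 3 counts, and its direction is unknown.
- The rejection rates rest on assumed drift. The calendar of 6 months' enrollment plus 3 months' follow-up giving 9 months leaves no explicit time for a gap. This suggests short intervals were expected, although it sets no limit for any patient.
- It would be too strong to say that the analyst could do nothing. Pain medication is recorded at baseline and Day 0, narcotics are converted to morphine equivalents, and dated consent would help bound the interval. An analysis restricted to same-day patients, or to those with stable medication, would be possible. It would examine the exposure but not supply the missing score.
- Medication, standard therapy and optional cementoplasty also act after ablation without a control. This point is a small part of that larger problem.
- The flowchart is not shown, and the Investigator Brochure and instructions for use were not available. A window stated only there cannot be excluded.

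None of this puts a pain score next to the ablation for patients with a gap.

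**Conclusion.** The point holds within limits. As written, the schedule lets the baseline visit precede Day 0 by any interval and plans no later pain score before ablation. Persisting pre-ablation change in those patients is then indistinguishable from device effect in the primary endpoint.

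The size cannot be determined from the documents. The range of 7% to 69% assumes no device effect, the plan's SD and correlation, 36 completers, and a persisting mean fall of 0.25 to 1.5 points across the whole sample. With a gap in only half the patients and falls of 0.5 or 1.0 points in them, it is 7% or 13%. If gaps are rare or short, the bias may be negligible.

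This is a secondary source of bias. It merits action because, unlike most of the confounding in a single-arm study, it can be removed at little cost, and a score not collected before ablation cannot be recovered.

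**What to change.** 1. In Tables A and 3, add the BPI worst-pain item on Day 0, before the procedure, when the baseline visit was on an earlier day.
2. In section 5.1, define baseline for the change score as the last worst-pain score before ablation.
3. Record the number of days from the baseline visit to Day 0.
4. Report a sensitivity analysis of the primary endpoint that uses the enrollment score as baseline.
5. State that the Day 0 score is used for analysis only, and that eligibility under criterion 8 remains as assessed at enrollment.

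The cost is one questionnaire item at a visit that already takes place, and a few sentences of text. The 36 evaluable and 52 enrolled stay the same under the stated SD and correlation. There is one statistical downside: if pain is only temporarily lower on Day 0, the new baseline could understate the effect. The sensitivity analysis would show this. The change removes only the pre-ablation part of the confounding; what happens between ablation and month 3 remains uncontrolled.
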